### **Compliance**

As interventions are personalised to the young person's needs across both the RBT and BAU groups, compliance and dose will be assessed from two perspectives. From a staff perspective we will assess fidelity to the components of the allocated tier in the RBT arm (case formulation, multi-agency meetings, reviews). For participants, the dose will be assessed in both arms as the proportion of planned meetings attended. Interactions between young people and staff are recorded on the same system between the different participating services. Records include planned meetings, who leads the meeting, staff member, trauma lead or psychologist and attendance. Compliance will be categorised into 5 quintiles, 0-19%, 21-40%, 41-60%, 61-80% and 81-100%. These will be employed in a dose response analysis. In addition, we will use this data to augment the micro-costing of the intervention.

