The efficacy trial design is a mixed method, two level, individually randomised controlled trial of a trauma informed intervention, Trauma Recovery Model Relationship Building Together (RBT), versus business as usual (BAU) for adolescents and young adults served by Bridgend Youth Services (youth justice, edge of care, youth development and early help). There are two levels to the study randomisation. Level one involves selecting staff to be trained in RBT. This allocation is done for all staff, after baseline staff data collection, and is conducted by an on-line independent secure randomisation service, Sealed Envelope Ltd. Consent will be sought from all eligible staff prior to randomisation. As allocations are done at the same time and because we want to maximise balance across the groups on key parameters, we will employ minimisation for the allocation of staff. Our aim will be to maximise balance in terms of service (youth justice, edge of care, children's services, youth development, and early help) and speciality (specialised staff versus generic staff). Provision has been made to conduct a second wave of staff randomisation and TRM training if there is a high turnover of staff throughout the trial – a high turnover is one that exceeds 30%.

Level two allocation involves the randomisation of young people to RBT or BAU. This will be conducted by research staff, using a secure, on-line randomisation service (Sealed Envelope Ltd). after informed consent has been taken and the baseline assessment completed and before any trauma screening has been conducted. The allocation will involve an equal probability of receiving RBT or BAU and will employ random permuted blocks of variable size (4, 6 or 8) with a random block seeded throughout. Randomisation will be stratified by service (youth justice, edge of care, children's services, youth development and early help), sex (male, female), and age group (<15 years, 15 years or more). Stratification variables have been chosen to ensure allocation is balanced across services, sex, and age as some workers specialise in working with older or younger males and females.

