We have used an effect size difference of 0.25 as an important difference; this equates to a difference in volume of offences of circa 12% over a 6-month period, similar effects as found in other psychologically focussed interventions to reduce recidivism in adolescent populations (Hodgkinson et al., 2021). To detect this difference or greater, using a two-sided test, alpha of 0.05 and power at 80% requires 506 young people to be followed-up at our primary endpoint, 6-months post-randomisation, 253 in each group. There is no reliable literature on pre- and post-test correlations for the SRDS, so we have erred on the side of caution and not accounted for this in the sample size calculation as an incorrect assumption increases the risk of an under-powered trial. If we take a potential loss to follow-up of 10%, similar to attrition found in our other studies of young people (Coulton S et al., 2023) this inflates the required baseline sample to 562. We have 73 potential interventionists, 35 randomised to control and 36 randomised to be trained in the intervention delivery. Each interventionist can manage a harmonic mean of 10 young people through the course of the study. To achieve our target, we would need to have at least 56 of these interventionists participating throughout the trial, 28 in each arm, thus allowing for a potential loss of interventionists of 17, 23% of those available.

Assuming only 80% of young people approached consent to take part as found in similar studies (Coulton S et al., 2023) means we would need to approach 702 young people, over the recruitment period. Allowing for a slower start of 20/ per month recruited over the first three months, means 36 will need to be recruited in each month between January 2024 and February 2025, allowing for a six-month follow-up for the interim report submitted in September 2025.

Analysis

All analysis is conducted using STATA 16 SE. Analysis will be conducted and presented in accordance with the CONSORT guidelines. The validity of randomisation will be explored by presenting baseline measures of central tendency and estimates of precision for continuous variables, and proportions for categorical variables broken down by allocated arm and stratification factors for both staff and participant samples.

Primary outcome analysis

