To avoid loss of efficiency missing outcome values will be imputed using multiple imputation, if the proportion of missing data is greater than 5% and less than 40%. Where there is less than 5% missing data, the proportion of missing data is considered negligible and missing observations will be excluded. Multiple imputation methods perform less well when the amount of missing data is substantial, if more than 40% of the primary outcome data are missing for the primary analysis the assumptions are less plausible. The interpretative limitations of the trial data will be discussed in the results section, where this is the case.

An initial variable reduction analysis will explore the relationship between all potentially prognostic baseline covariates and whether a follow-up data point is missing. Only variables where there is an association, p -value > 0.10 , will be included in the imputation model. The

association between the number of imputations will be dependent on the amount of missing data. As a minimum the number of imputations will be derived to ensure at least 96% statistical efficiency (*RE*) according to the formula below, where λ is the fraction of missing values and M is the number of repetitions (eq. 4).

$$RE = \left(1 + \frac{\lambda}{M}\right)^{-1}$$

The statistical model and assumptions made in the analysis of the primary outcome will also be implemented in the multiple imputation procedures. If it is suspected data is missing not at random or the pattern of missing data is associated with trial allocation, sensitivity analysis will be performed using a pattern mixture approach with mixed modelling and multiple imputation to compare the sensitivity of conclusions to varying assumptions about the missing value mechanism.

Intra-cluster correlations (ICCs)

The trial is individually randomised with stratification at the level of service, no ICC's will be calculated.

Compliance

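### The SAP's imputation model draws only on baseline variables screened against missingness, so it recovers little precision and cannot correct loss that runs through engagement; attendance records could be added cheaply

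*SAP*

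**What the plan says.** The SAP (Missing data) imputes the 6-month SRDS when between 5% and 40% of it is missing, and gives the reason: "To avoid loss of efficiency missing outcome values will be imputed using multiple imputation". It then sets out how the model is built: "An initial variable reduction analysis will explore the relationship between all potentially prognostic baseline covariates and whether a follow-up data point is missing". Only variables passing that screen enter, together with the primary analysis model. No variable measured after randomisation is mentioned. The printed cut-off is a p-value above 0.10, which would keep the variables *not* related to missingness; I read it as a slip for below 0.10.

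Eq. 1 (SAP, Primary outcome analysis) contains allocation, baseline SRDS, sex, age group and service. SDQ, GHQ12, SWEMWBS, BFRS, CSRI, ACE-Q, ethnicity and IMD are also available at baseline.

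On attendance, the protocol (Compliance) says "the dose will be assessed in both arms as the proportion of planned meetings attended". The source is the services' shared record system, not the follow-up questionnaire. The stated uses are compliance, dose and costing.

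The SAP adds a pattern-mixture sensitivity analysis if data are suspected to be missing not at random, or if missingness is associated with allocation. The protocol (Analysis) describes multiple imputation (MI) itself as a sensitivity analysis whenever more than 5% is missing, with complete-data, MAR and MNAR results all presented.

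**The concern.** Two things look wrong. First, when only the outcome is missing, imputing it from the covariates already in the analysis model adds no information. Any gain must come from auxiliaries that predict the outcome beyond eq. 1, yet the screen looks at prediction of missingness alone. The stated purpose and the construction do not match.

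Second, a plausible route to loss in this trial is disengagement after randomisation: a young person who stops attending may be harder to trace and may also offend differently. RBT aims to improve engagement, so this route could differ by arm. A baseline-only model cannot see it, although the services will hold a direct measure of it in both arms whether or not the questionnaire is returned. At stake is bias in the primary estimate that would be reported under a missing-at-random label.

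**Working it through.** **The plan's own figures.** Inputs from the SAP sample size section: "We have used an effect size difference of 0.25 as an important difference"; two-sided alpha 0.05; power 80%; 1:1 allocation. The normal approximation gives 2 x (1.96 + 0.842)² / 0.25² = 251.2, so 252 per arm. The t-based solution is 252.13, so 253 per arm and 506 in total. Then 506 / 0.90 = 562.2, and the SAP says "this inflates the required baseline sample to 562". Both figures reproduce.

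**Efficiency.** Let f be the fraction of outcomes missing and ρ² the partial R² of the auxiliaries for the 6-month SRDS beyond eq. 1. With many imputations,

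Var(MI) / Var(complete case) = 1 − f·ρ².

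The documents give no ρ², so I take 0 to 0.30 as an assumed range.

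| f | ρ² | variance ratio | effective N | power |
|---|---|---|---|---|
| 0.10 | 0 | 1.000 | 506 | 80.3% |
| 0.10 | 0.05 | 0.995 | 508 | 80.5% |
| 0.10 | 0.30 | 0.970 | 521 | 81.4% |
| 0.40 | 0 | 1.000 | 337 | 63.1% |
| 0.40 | 0.05 | 0.980 | 344 | 64.0% |
| 0.40 | 0.30 | 0.880 | 383 | 68.7% |

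Effective N is 562 × (1 − f) divided by the variance ratio. With no loss, 562 gives 84.2%. At 10% loss the auxiliaries recover about 5% to 28% of the lost information; the upper end is (521.4 − 505.8) / (562 − 505.8) = 28%. The formula is the same for a baseline auxiliary and for attendance.

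**Number of imputations.** The SAP's 96% rule requires M ≥ f × 0.96 / 0.04. That is 2.4 at 10% missing, so M = 3 suffices, and 9.6 at 40%, so M = 10.

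**Bias, by simulation.** 562 participants, 1,500 replicates, 20 imputations, true effect -0.25, and eq. 1 simplified to arm plus baseline SRDS. Assumed, not in the documents: each auxiliary has a coefficient of 0.3 SD on the outcome, RBT shifts attendance by 0.3 SD, and the log-odds of loss change by 1 per SD of the driving variable. Entries are bias in the estimated effect.

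| Loss depends on | Loss | Complete case | MI, eq. 1 terms | MI + baseline auxiliary | MI + attendance |
|---|---|---|---|---|---|
| attendance, same in both arms | 10% | 0.008 | 0.008 | 0.008 | 0.002 |
| attendance, same in both arms | 30% | 0.016 | 0.016 | 0.016 | 0.004 |
| attendance, one arm only | 10% | -0.029 | -0.029 | -0.029 | -0.002 |
| attendance, one arm only | 30% | -0.075 | -0.075 | -0.075 | -0.002 |
| baseline auxiliary, one arm only | 10% | -0.032 | -0.032 | 0.000 | -0.032 |
| baseline auxiliary, one arm only | 30% | -0.080 | -0.080 | -0.001 | -0.080 |

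MI on eq. 1 terms tracks complete case in every row, with a variance ratio of 1.00 to 1.01 at M = 20. At M = 3 the ratio is 1.03, slightly worse than not imputing. When loss is completely at random, a baseline auxiliary gives ratios of 0.994 (10% loss) and 0.978 (30%), and attendance gives 0.994 and 0.972. In the one-arm attendance setting the mean SE with attendance is 0.0770 against 0.0770 for complete case at 10% loss, and 0.0872 against 0.0871 at 30%.

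A second simulation gave bias of about -0.02 at 8% loss and -0.05 at 25% in the one-arm case. Across the runs, the same-mechanism case gave about 0.002 to 0.008 at roughly 10% loss.

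**The case against.** A reader might infer that the planned imputation simply reproduces the complete-case answer and recovers nothing. The documents do not support that. The candidate pool reaches well beyond eq. 1, and the last two rows of the table show a baseline auxiliary removing bias that runs through it. Nor would attendance rescue efficiency: it obeys the same bound, so the case for it is bias alone.

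The bias is also conditional. The documents give no effect of RBT on attendance and no relation of attendance to offending or to loss. At the planned loss with a common mechanism, 0.008 is about a tenth of the standard error (0.008 / 0.0768). These objections stand and set the size of the point.

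Two more stand in part. Attendance is not held on everyone, because the protocol (Ethics and registration) lets a participant withdraw completely and have their data removed. Planned contact also differs by service, from 6-8 weeks of crisis work to 6-9 months, so the proportion attended may not mean the same thing throughout. Service terms in the imputation model absorb differences in level, but not differences in slope.

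Finally, pattern-mixture analyses are planned. They help interpretation but leave the main imputation model unchanged. The SAP's version is conditional, and its allocation trigger is weak. Take an illustrative loss of 11.5% versus 9.0% with 281 per arm: the SE of the difference is √[(0.115×0.885 + 0.090×0.910)/281] = 0.0256, so z = 0.98. A 5% test (my assumption; the SAP sets no threshold) would then have about 16% power.

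**Conclusion.** The point holds as a cheap improvement. The SAP confines imputation to baseline variables chosen by their relation to missingness. That yields no precision gain if nothing outside eq. 1 is selected, and otherwise about 0.5% to 3% of variance at 10% loss, so the stated efficiency purpose is largely unmet.

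It also leaves bias from engagement-driven loss untouched. With a common mechanism in both arms this is trivial at the planned loss. If loss depends on attendance in one arm only, it is about 8% to 12% of the effect at 8-10% loss (0.02/0.25 to 0.029/0.25) and 20% to 30% at 25-30% loss (0.05/0.25 to 0.075/0.25). In these runs the one-arm bias lies away from the null and the common-mechanism bias towards it, so the error cannot be assumed conservative. All the bias figures rest on assumed engagement effects; they show what could happen, not what will.

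**What to change.** Amend the SAP's missing-data section to:

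- state the imputation model in full: every eq. 1 term, plus baseline variables that predict either the 6-month SRDS or its missingness, with the direction of the printed p-value rule corrected;
- add the proportion of planned meetings attended in months 0-6, taken from the service records, for all participants except complete withdrawers. It is an auxiliary in the imputation model only and stays out of eq. 1, because it is measured after randomisation;
- impute separately by arm, and set a minimum number of imputations well above the 3 that the 96% rule allows at 10% missing;
- report the complete-case estimate beside the imputed one;
- justify imputation by making missing at random more plausible, not by efficiency;
- settle with the protocol (Analysis) whether imputation is the main or a sensitivity analysis.

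The cost is SAP wording, a little more programming, and an attendance extract that the protocol's dose analysis already needs in both arms. The SE may rise slightly, although the simulations shown here found no material increase. The return depends on engagement effects that the documents do not give.

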Secondary outcomes will be assessed in a similar way by establishing diagnostic plots to identify the most appropriate regression approach; logistic for dichotomous outcomes, ordinal for ordered categorical outcomes, linear for continuous outcomes and fractional for proportions. Stratification factors and baseline covariates will be included within the model.

If the missing data exceeds 5%, sensitivity analyses will be performed using a pattern mixture approach and multiple imputation to compare the sensitivity of conclusions to varying assumptions about the missing data, particularly whether data is missing at random (MAR) or missing not at random (MNAR). This allows for an assessment of both random and systemic bias. Results based on complete data analysis, MAR and MNAR will be presented to explore the influence of missing data on outcomes observed.

We will conduct a Complier Average Causal Effects (CACE) analysis using an instrumental variable framework to explore the impact of compliance on the primary outcomes at different levels of compliance, both fidelity to the steps involved in each tier and quintiles of compliance. CACE weights the analysis by the ITT treatment effect by the proportion of compliance, this allows the estimation of unbiased treatment effects and maintains the allocation in the analysis.

Objective 3: For staff we will explore the differences between the groups in terms of overall wellbeing, perceptions of working in a trauma informed manner and confidence in working with young people who have experienced adverse childhood experiences derived from the SWEMWBS and ARTIC questionnaire at months 6 and 12 using linear regression adjusted for baseline score and service. Staff turnover and proportion absence will be assessed in a similar manner using fractional regression.

Objective 5: Stepwise regression analysis will be performed to model the relationship between pre-randomisation factors and demographics, on observed outcomes at 6 months.

Interaction terms with allocation arm will be included in the analysis, and a significance level of 0.1 will be used to determine which factors are to be included in the regression model. Pre-randomisation factors will include sex, age, ethnicity, IMD, family cohesion, adverse childhood experiences assessed by the service, and process measures, staff perceptions, staff confidence, and therapeutic alliance. The allocated arm will be included in this analysis as an interaction term.

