assessed by first looking at allocation by the three stratifying variables, service, sex and age group for participants and service and specialism for staff.

Baseline characteristics will be summarised by allocated group. Summary measures for the baseline characteristics of each group will be presented as mean and standard deviation for continuous (approximate) normally distributed variables, medians and interquartile ranges for non-normally distributed variables, and frequencies and percentages for categorical variables. Following CONSORT when comparing intervention and control groups we will not employ statistical testing.

If there is a large imbalance between groups on a specific variable, then that variable will be included in the analysis model. If there are systematic differences across multiple variables that are indicative of failed randomisation then it would be necessary to explore alternative analysis methods to estimate intervention effects, such as instrumental variable models, using allocation as the IV.

Missing data

The proportion of missing data and patterns of missingness will be examined for the primary outcome only, quantity of offences at 6-month post-randomisation. Levels of missing data will be reported along with any systematic occurrences of missing data observed in the dataset.

In trials some participants are inevitably lost to follow-up. Sample size estimation assumed 10% of patients would not provide an evaluable 6-month follow-up assessment. We will explore the mechanism of missing data to establish whether the data can be considered missing completely at random or missing at random. For each arm we will present baseline data for those followed-up at 6 months and those lost to follow-up and logistic regression analysis to explore for any systematic differences between the allocated group. If no predictor variables emerge from the regression model then the missing data can be classed as missing at random.

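### The SAP states the imputation-model inclusion rule backwards and makes the missing-not-at-random analysis conditional, where the protocol promises it whenever missing data exceed 5%

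*SAP*

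**What the plan says.** All the SAP text is in its Missing data section.

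- **Choosing imputation variables.** Baseline covariates are screened against missingness: "An initial variable reduction analysis will explore the relationship between all potentially prognostic baseline covariates and whether a follow-up data point is missing". Then: "Only variables where there is an association, p -value > 0.10 , will be included in the imputation model". A later sentence says that the model and assumptions of the primary analysis also apply in the imputation. That model (SAP, Primary outcome analysis, eq. 1) contains allocation, baseline SRDS, sex, age group and service.
- **Naming the mechanism.** The aim is to "establish whether the data can be considered missing completely at random or missing at random". The rule is: "If no predictor variables emerge from the regression model then the missing data can be classed as missing at random".
- **When the MNAR analysis is run.** The SAP's condition for the pattern-mixture sensitivity analysis is: "If it is suspected data is missing not at random or the pattern of missing data is associated with trial allocation". The protocol (Analysis, Objective 2) instead performs pattern-mixture and multiple-imputation sensitivity analyses if missing data exceed 5%, and adds: "Results based on complete data analysis, MAR and MNAR will be presented to explore the influence of missing data on outcomes observed".
- **Number of imputations.** "As a minimum the number of imputations will be derived to ensure at least 96% statistical efficiency". Eq. 4 gives the relative efficiency, "where λ is the fraction of missing values and M is the number of repetitions".

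Imputation is used when between 5% and 40% of primary-outcome values are missing. The sample size assumes 10% loss at month 6.

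**The concern.** The inclusion rule contradicts itself: its words ask for an association and its symbol asks for none. An analyst who codes the symbol builds an imputation model that lacks the covariates most useful for making MAR plausible. The screen also looks only at whether the outcome is missing, not at whether a covariate predicts its value, although covariates that do both are the ones that remove bias.

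The mechanism rule and the sensitivity trigger compound this. A regression of missingness on observed baseline data cannot show whether loss depends on the unseen outcome. In a trial of self-reported offending it is plausible (an assumption, not a statement in the documents) that those who offend more are harder to follow up. Under the SAP, a finding of no predictors could lead to the MNAR analysis being skipped, although the protocol commits to it.

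Planned attrition lies inside the imputation band, so these rules bear on the primary outcome. Correcting them after outcome data are seen would be a post hoc change.

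**Working it through.** **1. Will the rules be used?** The plan's own figures: 506 followed up, 10% loss, so 506 / 0.9 = 562.2, against 562 stated. About 562 − 506 = 56 primary outcomes are expected to be missing. Ten per cent lies above the protocol's 5% trigger and within the SAP's 5–40% band.

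**2. What the printed inequality does.** 1,000 simulated datasets, n = 562, about 10% missing. One covariate predicts missingness (assumed log-odds 0.6 per SD) and one is unrelated. Each is tested by comparing its mean in those missing and those observed.

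| Rule | True predictor kept | Unrelated covariate kept |
|---|---|---|
| p > 0.10 (as printed) | 0.9% | 90.7% |
| p < 0.10 | 99.1% | 9.3% |

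The exact percentages depend on the assumed strength; the direction does not.

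**3. What an omitted predictor could cost (illustration only).** Suppose that those lost in one arm are 1 SD worse on a dropped covariate outside eq. 1, and that the outcome changes by 0.4 SD per SD of that covariate given the eq. 1 variables. Then bias ≈ proportion lost × 1 × 0.4:

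- 10% lost: 0.04 SD, and 0.04 / 0.25 = 16% of the target effect.
- 20% lost: 0.08 SD, and 0.08 / 0.25 = 32% of the target effect.

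The 1 SD gap, the slope of 0.4 and the one-arm pattern are all assumed.

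**4. The mechanism rule and the MNAR trigger.**

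| Regression of missingness on baseline data | Compatible with |
|---|---|
| Predictors emerge | MAR or MNAR; evidence against missing completely at random (MCAR) |
| No predictors emerge | MCAR, MAR or MNAR |

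Neither row excludes MNAR. Nor does the allocation condition: equal loss in both arms can hide different reasons for loss.

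| | Condition for the MNAR analysis | At 10% missing |
|---|---|---|
| Protocol | Missing data exceed 5% | Run and presented |
| SAP | MNAR suspected, or missingness related to allocation | Run only if a condition is judged met |

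**5. Number of imputations.** Setting 1 / (1 + λ/M) ≥ 0.96 gives M ≥ λ / (1/0.96 − 1) = 24λ.

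| λ | 24λ | Smallest M |
|---|---|---|
| 0.05 | 1.2 | 2 |
| 0.10 | 2.4 | 3 |
| 0.20 | 4.8 | 5 |
| 0.40 | 9.6 | 10 |

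At λ = 0.10, M = 3 gives efficiency 0.968, and M = 2 gives 0.952 and fails.

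Monte Carlo SD of the pooled estimate, in standard errors (SE), taking the fraction of missing information as 0.10: √(B/M) with B = 0.10 / (1 + 1/M).

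- M = 3: B = 0.075, √0.025 = 0.158.
- M = 20: B = 0.0952, √0.00476 = 0.069.
- M = 50: B = 0.0980, √0.00196 = 0.044.

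For a result exactly at z = 1.96 with M = 3, about two Monte Carlo SDs either way (1.96 × 0.158 = 0.31) gives z from 1.65 to 2.27, p about 0.10 to 0.02. One SD gives z from about 1.80 to 2.12, p about 0.07 to 0.03. With M = 20, about two SDs (1.96 × 0.069 = 0.14) gives z from 1.82 to 2.10, p about 0.07 to 0.04.

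**The case against.** The strongest reply is that the inequality is a slip. The sentence itself speaks of an association, and the SAP's Further analyses section uses a 0.1 significance level to admit factors to another model. A reader might infer that the authors mean to discard useful predictors; the documents do not support that. But the rule is the operative instruction for imputing the primary outcome, and followed as printed it does the opposite of its purpose.

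A second reply is that the primary-analysis model is carried into the imputation, so allocation, baseline SRDS, sex, age group and service are not lost. This stands and limits the harm. It does not settle the matter, because the restriction to screened variables says something different, and covariates outside eq. 1 are still selected the wrong way round.

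Third, data that are MCAR also satisfy MAR, so the label given to the no-predictors case is imprecise rather than false. Imputation is triggered by the percentage missing, so relabelling alone would not change the primary analysis. This also stands. What matters is that the result should not decide whether the MNAR analysis is run.

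Fourth, a reader might infer that the SAP plans three imputations, or that eq. 4 is wrong. Neither holds: the formula is a valid efficiency criterion, it is stated as a minimum, and no number is fixed.

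**Conclusion.** Two faults stand and should be corrected before outcome data are seen. The inclusion rule is wrong as written and clashes with the sentence that brings in the primary-analysis model. The SAP also makes conditional an MNAR analysis that the protocol promises above 5% missing, and its regression on observed data cannot supply the missing condition.

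The direction of the first fault is certain. Its effect on the treatment estimate is not quantifiable from the documents: the 0.04 and 0.08 SD figures are illustrations on assumed inputs, and a reader should not infer that a bias of that size is expected. The second fault needs no assumption beyond the planned 10% loss.

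The number of imputations is a minor matter. The floor permits M = 3 at 10% missing, with Monte Carlo noise of about 0.16 SE. The z range of 1.65 to 2.27 is a two-SD range for a result exactly at the threshold with M at its minimum; it does not show that the trial's p-value will be unstable.

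**What to change.** In the SAP's Missing data section:

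1. State that the imputation model always includes allocation, baseline SRDS, service, sex and age group, plus any baseline covariate associated (p < 0.10) with either missingness or the month-6 outcome. This corrects the sign and removes the conflict over which sentence governs.
2. Replace the sentence that classes data as missing at random with: MAR is assumed and cannot be established from observed data.
3. Run the pattern-mixture analysis whenever missing data exceed 5%, and present complete-data, MAR and MNAR results, as the protocol says.
4. Minor: keep eq. 4 as a floor but pre-specify a larger fixed number of imputations, for example 20 or more (0.07 SE of Monte Carlo noise at 10% missing information). Fifty would give 0.04 SE; the choice between them is a preference, as is imputing separately by arm.

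The cost is a few sentences and minutes of computing. No data collection or design feature changes.
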